Subjects will be treated with talimogene laherparepvec until a CR is achieved, all injectable tumors have disappeared, confirmed PD per modified irRC-RECIST, intolerance of study treatment, until they have received 6 cycles and in the investigator's

opinion no further talimogene laherparepvec injection would be of clinical benefit, or the investigator determines it is in the best interest of the subject to discontinue treatment (eg, rapid clinical deterioration or worsening symptomatic disease requiring alternative systemic anti-cancer therapy), whichever occurs first. After 6 cycles have been received, the subject may be a candidate for up to 6 additional cycles of talimogene laherparepvec (Section 3.1.3). In Part 2, if the subject has completed 12 cycles of talimogene laherparepvec, the subject may be a candidate for additional cycles of talimogene laherparepvec, up to a total of 35 cycles, if there are still **cutaneous, subcutaneous, or nodal** lesions suitable for injection provided that in the opinion of the investigator, the subject has clinical benefit and provided sponsor medical monitor approval has been obtained by the investigator. Due to the mechanism of action of talimogene laherparepvec, subjects may experience growth in existing tumors or the appearance of new tumors prior to maximal clinical benefit of talimogene laherparepvec. Therefore, talimogene laherparepvec dosing should continue provided that the subject has no evidence of confirmed PD per modified irRC-RECIST (Appendix D) and is able to tolerate treatment. In Part 2, in the event that talimogene laherparepvec was discontinued for reasons other than toxicity (e.g., no further injectable lesion), and subject subsequently developed progressive disease or injectable disease while still on pembrolizumab, talimogene laherparepvec may be resumed if investigator and medical monitor are in agreement. If the liver is to be injected, subjects must be monitored for a minimum of 6 hours after each talimogene laherparepvec injection.

The concentration, start date, volume, and lot number of talimogene laherparepvec are to be recorded on the CRF.

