If talimogene laherparepvec dosing is delayed by more than 6 weeks from the date of the planned dose (ie, approximately 9 weeks from the previous dose) for reasons other than treatment-related toxicity, the case must be reviewed by the Amgen medical monitor in conjunction with the investigator to determine if the subject can resume talimogene laherparepvec therapy.

Talimogene laherparepvec is to be permanently discontinued for subjects meeting any of the following criteria:

- Subject developed a DLT during the DLT evaluation period (please refer to Section 3.1.4.3).

- The subject, for any reason, requires treatment with another anti-cancer therapeutic agent for treatment of the study disease (other than the exceptions noted in Section 6.6). In this case, discontinuation from the treatment occurs immediately upon introduction of the new agent.
- Confirmed PD occurs as defined per modified irRC-RECIST ([Appendix D](#)).
- A grade 2 or greater immune-mediated adverse event (with the exception of vitiligo) or allergic reactions attributed to talimogene laherparepvec that would require a dose delay of greater than 6 weeks from the date of the planned dose (ie, approximately 9 weeks from the previous dose).

NOTE: immune-mediated glomerulonephritis, vasculitis, and pneumonitis and exacerbation of psoriasis have been observed in subjects receiving talimogene laherparepvec in clinical trials. Most of these subjects had a history of other autoimmune disease and/or prior treatment with agents that offered plausible alternative etiologies, however, immune-mediated adverse events can potentially involve any organ system.

- Any other talimogene laherparepvec-related non-hematologic or hematologic toxicities Grade 3 or greater occur that, in the opinion of the investigator, would require a dose delay of greater than 6 weeks from the date of the planned dose (ie, approximately 9 weeks from the previous dose).
- A female subject becomes pregnant or fails to use acceptable method(s) of effective contraception (for those subjects who are able to conceive).
- A female subject breast feeds while on study treatment.
- Concurrent medical illness that, in the judgment of the investigator, would make continued treatment with talimogene laherparepvec dangerous for the subject.

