Local palliative radiation treatment for relief of various symptoms, including but not limited to bleeding or pain associated with the underlying disease will be permitted at any time during the study. Subjects with local symptoms suggestive of disease progression should be evaluated for tumor response per modified irRC-RECIST (see [Appendix D](#)) prior to the administration of palliative radiotherapy. If a subject undergoes local radiation, the investigator or designee should notify the sponsor medical monitor as soon as possible and the treatment should be recorded in the source document and CRF.

If a subject demonstrates evidence of new or worsening CNS metastases, talimogene laherparepvec and/or pembrolizumab treatment should be withheld and the investigator or designee should notify the sponsor's medical monitor as soon as possible. Subjects may be allowed to remain on study after discussion between the sponsor medical monitor and the investigator to determine the appropriateness of treatment resumption provided CNS lesions can be treated with stereotactic radiotherapy (including Gamma Knife), whole brain radiation, or craniotomy and if there is no change in the baseline ECOG performance status. Subjects may be allowed to resume talimogene laherparepvec treatment per Section 6.2.1 following treatment of CNS metastases while receiving dexamethasone or a similar corticosteroid at no more than 1.5 mg dexamethasone (or 10 mg prednisone) per day. If higher doses of corticosteroid are used, talimogene laherparepvec must be held until that dose level is reached during the period of steroid tapering.

If a subject with confirmed PD (ie, two consecutive tumor assessments at least 4 weeks [28 days] apart demonstrating PD) is clinically stable or clinically improved, and there is no further increase in tumor burden at the confirmatory assessments (assessed by the

investigator and site radiologist, if applicable), an exception may be considered to continue treatment upon consultation with the sponsor medical monitor.

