- ^x Radiographic tumor imaging: During treatment, radiographic tumor imaging will be performed independent of treatment cycle at week 10 (\pm 1 week) and then every 9 weeks (\pm 1 week) until confirmed progressive disease (PD) per modified immune-related response criteria (irRC) simulating RECIST version 1.1 (irRC-RECIST) ([Appendix D](#)). Radiographic imaging is required at the safety follow up visit if the subject ended treatment prior to documentation of confirmed PD per modified irRC-RECIST and has not had radiographic tumor imaging performed within 9 weeks (\pm 1 week) of the visit. Every effort should be made to complete radiographic assessments during the long-term follow-up every 12 weeks (+ 1 week) until documented confirmed PD per modified irRC-RECIST, start of new anticancer treatment, death, or end of study, whichever occurs first, for subjects discontinuing study treatment for any reason other than confirmed PD. Response (complete response [CR], or partial response [PR]) or disease progression to be confirmed by second consecutive radiographic assessments no less than 4 weeks from the date of the first documented response or disease progression. Note: Confirmation of disease progression is required only in the absence of rapid clinical deterioration (ie, rapid decline in performance status) or symptomatic disease requiring rapid initiation of alternative systemic anti-cancer therapy.
- ^y To be performed if required by site for assessment of the intrahepatic lesion injection location. **As of Protocol Amendment 6 (dated 26 October 2021), intrahepatic injections of talimogene laherparepvec and liver biopsies are no longer performed in this study.**
- ^z If no progression is seen after a total of 12 cycles, a total of 35 cycles of talimogene laherparepvec, at maximum tolerated dose if known or otherwise previously received dose, every 21 (\pm 3 days) may be administered, or the subject may proceed to alternative therapies depending on investigator discretion. Dosing with talimogene laherparepvec beyond 12 cycles may be done if in the opinion of the investigator, the subject is deriving clinical benefit.

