## Best overall response (BOR) per Modified irRC-RECIST

Best overall response (BOR) of complete response (CR), partial response (PR), stable disease (SD), progressive disease (PD) or un-evaluable (UE) will be derived based on investigator assessment using modified irRC-RECIST as defined in protocol Appendix D.

Overall visit response assessments occurring after the start of the first subsequent anticancer therapy **will not be included. With the exception of a PD observation, the overall visit response** occurring on or after complete or partial removal/reduction of any target lesion which contained cancer on pathology evaluation or pathology results were unknown, will not be included. Consecutive confirmation of CR, PR, and PD is required where the second overall response must be at least 28 days from the first, the only exception being when the investigator reports that an initial PD cannot be confirmed due to rapid clinical deterioration. The following will be considered a confirmed PR: CR followed by PR or PR followed by CR.

BOR is defined as the best visit response in the following order: CR, PR, SD, PD, or UE (see [Table 1](#)). BOR is defined as SD if the best overall visit response is an unconfirmed CR or PR, and UE if it is either SD earlier than 77 days after first dose date or an unconfirmed PD when confirmation of PD is required (ie, initial PD without rapid clinical deterioration).

Table 1. Matrix of Determining BOR per Modified irRC-RECIST

Visit Overall Response Sequence	Examples	Best Overall Response	Confirmation specifications
*, CR, CR,*	PR, CR, CR CR, CR, PD	CR	The confirmatory CR must be at least 4 weeks (28 days) later; a subsequent CR within 28 days will not be valid for

			confirmation and will be ignored; the CR will also not be confirmed if there is a subsequent PR/SD/PD at any time prior to the next CR.
* , PR, PR, *  * , PR, CR/PR, non-CR, *  * ,CR, PR,*	PR, PR, PD PR, CR, PD  CR, PR, PD	PR	Criteria for BOR=CR not met. The confirmatory PR/CR must be no less than 4 weeks (28 days) later; a subsequent PR/CR within 28 days will not be valid for confirmation and will be ignored; the PR will also not be confirmed if there is a subsequent SD/PD at any time prior to the next PR/CR.
* , SD, *  * ,CR, non-PR/CR, *  * ,PR, non-PR/CR, *	CR PD, CR PR PD, PR, SD SD PD,SD,PD	SD	Criteria for BOR=CR or PR not met. SD must be $\geq 77$ days from the date of first dose; however, this is not required for an unconfirmed CR/PR.

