* ,PD, PD, *  * , PDr, *  PDr = PD with concurrent or subsequent rapid clinical deterioration as the reason for ending radiographic follow-up.	PD, PD PD, SD, PD, PD PDr	PD	Criteria for BOR= CR, PR, or SD not met. The confirmatory PD must be no less than 4 weeks (28 days) later unless there is rapid clinical deterioration; PDr does not require confirmation; a subsequent PD within 28 days will not be valid for confirmation and will be ignored.
* , SD, *  PD	SD UE, SD PD UE, PD	UE	Criteria for BOR=CR, PR, SD, or PD not met. SD must be $< 77$ days from the date of first dose.

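### Best overall response is not cut off at confirmed progression, so a subject treated past it can count as a responder in the primary ORR after already having a PFS event

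*SAP*

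**What the plan says.** **Response.** SAP section 5 states: "BOR is defined as the best visit response in the following order: CR, PR, SD, PD, or UE". It sets aside two kinds of visit. The first is "Overall visit response assessments occurring after the start of the first subsequent anticancer therapy". The second, except for PD, is a visit "occurring on or after complete or partial removal/reduction of any target lesion which contained cancer on pathology evaluation" or whose pathology is unknown. The ORR definition stops the clock only at subsequent anticancer therapy or data cutoff. In SAP Table 1 the PR patterns begin with a wildcard, so any visits may come before PR, PR. The PD row applies only when "Criteria for BOR= CR, PR, or SD not met".

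**PFS and DOR.** The SAP counts confirmed PD or death as the PFS event. DOR runs from the first visit of a confirmed response to PD or death, whichever is earlier.

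**Treatment at and after progression.** Protocol 6.2.1.2 lists as a reason for permanent discontinuation of talimogene laherparepvec: "Confirmed PD occurs as defined per modified irRC-RECIST". Protocol 6.6 covers subjects with confirmed PD who are clinically stable or better and whose tumor burden has not grown further at the confirming assessment. For them, "an exception may be considered to continue treatment upon consultation with the sponsor medical monitor". Protocol 6.2.1.1 adds for Part 2 that, if the injections were stopped for a reason other than toxicity and the "subject subsequently developed progressive disease or injectable disease while still on pembrolizumab, talimogene laherparepvec may be resumed" by agreement of the investigator and medical monitor. It does not say whether that PD must be confirmed.

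**Imaging.** Footnote x to Protocol Tables 12 and 13 schedules on-treatment scans "until confirmed progressive disease (PD) per modified immune-related response criteria". No schedule is given for subjects treated beyond that point.

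**The concern.** A subject who has progressed twice and is kept on study drug by exception can still be credited with a response. Three things follow.

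- The primary ORR and PFS disagree about the same subject: the PFS failure comes before the response begins.
- DOR has no clear end for that subject, because the PD already on record precedes the response. DRR inherits the problem, since it is built on DOR.
- Scans after confirmed PD fall outside the regular schedule. They come from subjects selected for doing well, in an open-label trial with investigator-assessed response.

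The final rule in a full arm is 6 or more confirmed responders of 21, so a single subject can decide it. SAP Table 9-1 lists no sensitivity analysis that would show whether this had happened.

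**Working it through.** **1. Applying the written rules to visit sequences**

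| Visits (study day) | BOR as written | BOR cut at confirmed PD | PFS event |
|---|---|---|---|
| PD (64), PD (127), PR (190), PR (253) | PR | PD | day 64 |
| PD (64), PD (92), PR (127), PR (155) | PR | PD | day 64 |
| PD (64), PR (127), PR (190) | PR | PR | none |

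Only sequences with a confirmed PD before the response change. A response after one unconfirmed PD counts either way.

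**2. The plan's own figures**

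Inputs (Protocol 10.2, SAP 3.2): 10 subjects in Stage 1; continue with 2 or more responders; 11 more in Stage 2; reject H0 with 6 or more of 21; H0 10%, H1 40%.

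P(reject) = sum over x = 2 to 10 of C(10,x) p^x (1−p)^(10−x) × P[Bin(11,p) ≥ 6−x].

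At p = 0.10 the terms are:
- x = 2: 0.1937 × 0.0185 = 0.00359
- x = 3: 0.0574 × 0.0896 = 0.00514
- x = 4: 0.0112 × 0.3026 = 0.00338
- x = 5: 0.0015 × 0.6862 = 0.00102
- x of 6 or more: 0.00015

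The sum is 0.0133. At p = 0.40 the result is 0.884. The probability of stopping at Stage 1 is 0.736 under H0 and 0.046 under H1. All four match the stated 1.3%, 88.4%, 73.6% and 4.6%.

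**3. One subject**

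The ordinary exact (Clopper-Pearson) 95% lower limit is 8.2% for 5/21 and 11.3% for 6/21, on either side of the 10% null.

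**4. A rate of late responders**

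Let q be the proportion responding after confirmed PD among subjects who had not responded before it. The documents give no value, so 2% and 5% are assumptions. With 10% ORR up to confirmed PD, the counted rate is 0.10 + 0.90q:
- q = 2%: 0.10 + 0.018 = 0.118
- q = 5%: 0.10 + 0.045 = 0.145

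Two treatments of the Stage 1 gate bracket the answer. In (a), late responses count at the gate, so the formula above is used with p = 0.118 or 0.145. In (b), the gate sees only the 10% rate. Then X ~ Bin(10, 0.10) must be at least 2, late responders L ~ Bin(10−X, q) are added afterwards, Stage 2 contributes Y ~ Bin(11, 0.10 + 0.90q), and H0 is rejected if X + L + Y ≥ 6.

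| q | (a) counted at gate | (b) not counted at gate |
|---|---|---|
| 0 | 1.3% | 1.3% |
| 2% | 2.8% | 2.5% |
| 5% | 6.7% | 5.1% |

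**5. Timing and reach**

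On scans at weeks 10, 19, 28 and 37, PD, PD, PR, PR has its first PR at week 28 and its confirmation at week 37. The futility look needs at least 20 weeks of potential follow-up and the primary analysis at least 29. With the minimum 4-week confirmations the sequence can fit weeks 10, 14, 19 and 23. Case (b) is therefore the more likely for the gate, but (a) is possible.

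Part 2 has 53 subjects. Two full arms take 2 × 21 = 42; three would take 63. At most two arms can have reached 21.

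**The case against.** **Late response is part of these criteria.** Protocol Appendix D says they were adapted so that clinically stable subjects can be treated past progression. It bases best response on change in tumor burden from baseline, setting aside an early increase or new lesions. Several SAP Table 1 examples begin with PD. Counting any response before new therapy or data cutoff is a coherent definition. This stands as far as it goes, but neither text says that a response after *confirmed* PD counts. Appendix D presents confirmation of PD as the means of catching late responders, and none of the Table 1 examples has a response after two consecutive PDs. The point is to choose and state a rule, not to show that the present one is indefensible.

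**The resumption clause mostly concerns unconfirmed PD.** A reader might infer from Protocol 6.2.1.1 that responses to re-treatment at progression generally enter ORR. The documents do not support that. Resumption requires the subject to be on pembrolizumab, which footnote aa to Tables 12 and 13 continues until confirmed PD. Outside the 6.6 exception, the earlier PD would usually be unconfirmed, is not a PFS event, and would still count under the fix. The route matters only where that PD was confirmed. Nor do the documents describe such treatment as salvage: it is the same study drugs under protocol provisions.

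**The case is narrow.** It needs confirmed PD, consultation with the medical monitor, then a fall to at least 30% below baseline on two assessments 28 or more days apart, off the regular scan schedule and before any new therapy. This also stands, and it limits the size of the point.

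**Conclusion.** The gap in the rules is real and touches the primary endpoint. As written, PD, PD, PR, PR is a confirmed responder for ORR and a failure for PFS, with DOR undefined. The clear route to it is the Protocol 6.6 exception.

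The effect is probably small, because such cases should be uncommon, but it could decide an arm that reached 21 subjects with five other responders. Under assumed late-response rates of 2% and 5%, the chance of a false rejection is about 2.5–2.8% and 5.1–6.7% instead of 1.3%. At 2% it lies at or just above the 2.5% limit. These figures rest on the assumed rates, a 10% ORR up to confirmed PD, and a full 10 + 11 arm.

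A reader might infer that the stated error rate is wrong, or that it is inflated in all six arms. Neither follows: the design figures reproduce exactly, and no more than two arms can have reached the final rule at 21. Nor does the point argue against crediting a response after an unconfirmed initial PD.

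**What to change.** In SAP section 5:

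- State that BOR and ORR use visits up to and including the first confirmed PD, or PD with rapid clinical deterioration.
- State that a response after an initial PD that was not confirmed still counts.
- State that DOR ends at the first PD after the response, or at death.
- List any response after confirmed PD, and enter in Table 9-1 an ORR that includes them as a sensitivity analysis.

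The cost is a few sentences, one listing and one extra estimate per arm. Sample size, thresholds and stated operating characteristics stay as they are. The downside is that the rare genuine late responder leaves the primary ORR; the sensitivity analysis keeps that subject visible. If the sponsor does intend to count such responses, it should say so and make the ORR cut at confirmed PD the sensitivity analysis.

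Separately, Protocol 6.2.1.1, 6.2.1.2 and 6.6 should be reconciled on treatment at and after confirmed PD. No view is taken here on which rule should apply.

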### **Duration of Response (DOR)**

Duration of response is defined as the time from the date of an initial response that is subsequently confirmed to the earlier of PD (see definition of BOR per modified irRC-RECIST) or death. Subjects who have not ended their response at the time of analysis will be censored at the last evaluable tumor assessment before start of the first subsequent anticancer therapy.

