7.2.3.2 Survival Follow-up

All subjects who permanently discontinue study drug for any reason other than withdrawal of full consent will be contacted by clinic visit or telephone to assess survival, talimogene laherparepvec-related adverse events, and initiation of additional anti-tumor treatment. For subjects in the combination treatment cohort, the long-term follow-up starts after the discontinuation of whichever study drug is discontinued last.

For Part 1, contact for all subjects will be attempted approximately every 12 weeks (± 28 days) following the safety follow-up visit until death, subject withdrawal, or up to approximately 24 months after the date of the last subject enrolled in Part 1. Subjects in Cohort 5 and 6 will be followed approximately 24 months after the last subject enrolled in their cohort in Part 1, or approximately 24 months after the last subject enrolled with their tumor type in Part 2, whichever is later.

For Part 2, contact for all subjects will be attempted approximately every 12 weeks (± 28 days) following the safety follow-up visit until death, subject withdrawal, or up to approximately 24 months after the date of the last subject enrolled in that tumor cohort.

[figure not shown]
Radiographic Tumor Assessment: Every effort should be made to complete radiographic assessments approximately every 12 (+1) weeks during the long-term follow-up until documentation of PD per modified irRC-RECIST ([Appendix D](#)), start of new anticancer treatment, death, or end of study, whichever occurs first, for subjects discontinuing treatment for any reason other than PD. In Part 2, clinical tumor assessment, if applicable, should be performed and documented at these timepoints as well. Response (CR, or PR) or disease progression to be confirmed by second consecutive radiographic assessments no less than 4 weeks from the date of the first documented response or disease progression. Note: Confirmation of disease progression is required only in the absence of rapid clinical deterioration (ie, rapid

[figure not shown]
decline in performance status) symptomatic disease requiring rapid initiation of alternative systemic anti-cancer therapy.

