### **Durable Response Rate (DRR)**

Durable response rate is defined as the percent of subjects with a CR or PR per modified irRC-RECIST with a DOR  $\geq$  6 months. One month will be calculated based on 365.25 days per year.

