### **Progression-free survival (PFS)**

PFS is defined as the interval from first dose date to the earlier event of confirmed PD or death from any cause. Subjects without an event will be censored at the latter of their last evaluable tumor assessment if available; otherwise will be censored on Study Day 1.

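### Duration of response has no cut-off at new anticancer therapy for deaths, so some responders who switch therapy count as durable if they later die but not if they live

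*SAP*

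**What the plan says.** Under Duration of Response in SAP section 5, a response lasts from its first confirmed documentation "to the earlier of PD (see definition of BOR per modified irRC-RECIST) or death". The next sentence sets the censoring. "Subjects who have not ended their response at the time of analysis" are the only subjects it covers, and they "will be censored at the last evaluable tumor assessment before start of the first subsequent anticancer therapy".

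The reference to the BOR definition matters because that definition limits which progressions count. "Overall visit response assessments occurring after the start of the first subsequent anticancer therapy" are left out, and progression needs a second assessment at least 28 days later unless rapid clinical deterioration prevents it. Protocol 7.2.3.2 also ends off-treatment imaging at documented progression, "start of new anticancer treatment, death, or end of study, whichever occurs first". Survival contacts continue under the same section, in Part 2 until about 24 months after the last enrolment in the tumor cohort.

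DRR is built directly on DOR: "Durable response rate is defined as the percent of subjects with a CR or PR per modified irRC-RECIST with a DOR" of at least 6 months, with a month taken from a 365.25-day year. SAP Table 9-2 reports DRR as a proportion with a 95% CI and DOR by Kaplan-Meier. It lists no sensitivity analysis for either.

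**The concern.** Once a responder starts other anticancer therapy, a progression first seen afterwards cannot end the response, but a death can. A subject who dies has ended the response under the first DOR sentence, and so falls outside the censoring sentence. A subject still alive falls inside it and is cut back to the last scan before the switch. Two responders with identical scans and the same switch date can therefore be classified oppositely, and the one who dies gets the favourable result.

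In that case DRR credits unscanned time on another therapy as continuing response to study treatment. It can also rise between the primary analysis (at least 29 weeks of potential follow-up) and the final analysis (after survival follow-up) with no new tumor data, simply because switched responders have died in between. In the Kaplan-Meier estimate of DOR, switchers who die stay at risk until death, while living switchers leave at their last scan before the switch.

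**Working it through.** **The plan's own figure.** The documents give no expected value or power for DRR or DOR. The only design figures concern the Part 2 response-rate test (SAP 3.2): continue with 2 or more responders in 10, reject with 6 or more in 21. The rejection probability is the sum over k = 2 to 10 of Bin(10, k, p) × P(Bin(11, p) ≥ 6 − k).
- At p = 0.10 it is 0.0133, with probability of stopping at Stage 1 of 0.7361.
- At p = 0.40 it is 0.8839, with probability of stopping at Stage 1 of 0.0464.

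These match the stated 1.3%, 88.4%, 73.6% and 4.6%. The test is not affected by this point, because the SAP's ORR definition is itself cut at the start of subsequent therapy.

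**The durability threshold.** 6 × 365.25 / 12 = 182.625 days, or 26.1 weeks.

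**Worked subject.** Scans follow the protocol schedule (week 10, then every 9 weeks). The clinical course is assumed: response at week 10, confirmed at week 19, last evaluable scan at week 28, new therapy at week 30. No progression is countable, meaning neither confirmed nor accompanied by rapid clinical deterioration.
- Alive at analysis: censored at week 28. DOR = (28 − 10) × 7 = 126 days; 126 / 30.4375 = 4.1 months. Not durable.
- Death at week 50: DOR = (50 − 10) × 7 = 280 days; 280 / 30.4375 = 9.2 months. Durable.
- The classification changes for a death at or after week 10 + 26.1 = 36.1.

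**Checking the threshold in days.** Assumed: response day 70, last scan day 133, no progression, new therapy day 140.

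| Status | DOR (days) | Months | Durable? |
|---|---|---|---|
| Alive | 133 − 70 = 63 (censored) | 2.07 | No |
| Died day 230 | 160 | 5.26 | No |
| Died day 260 | 190 | 6.24 | Yes |
| Died day 300 | 230 | 7.56 | Yes |
| Died day 400 | 330 | 10.84 | Yes |

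If DOR is instead censored at the last scan before the switch for everyone, all five rows become 63 days, 2.07 months, not durable.

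**Conditions for a reclassification.** All three must hold:
1. No countable progression precedes the switch.
2. The last evaluable scan before the switch is less than 182.6 days after first response; otherwise the living subject is durable too.
3. Death is at least 182.6 days after first response and is observed by the data cutoff.

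**Size per subject.** One reclassified subject is 1/21 = 4.8 points in a full arm and 1/10 = 10 points in a Stage 1 arm. For example, 4/21 = 19.0% (95% CI 5.4 to 41.9) becomes 3/21 = 14.3% (3.0 to 36.3). These intervals are Clopper-Pearson, which the SAP names for Part 1; I assume the same for Part 2.

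**The case against.** The strongest defence is that the plan already deals with much of the likely route. A responder who progresses and moves quickly to other treatment may qualify as progression with rapid clinical deterioration, which needs no confirmation under SAP Table 1. Protocol 3.5.1 describes such deterioration broadly enough to include needing other therapy. In those subjects the response ends at the first progression scan whether they live or die, and the asymmetry disappears. This stands, and it reduces the number of cases. It does not remove them: a responder may switch without progression, or with a first progression that is not reported as rapid deterioration and whose confirming scan would fall after the switch.

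The sponsor may also have meant the censoring date to apply to everyone who starts new therapy. The SAP's cut-offs for ORR, lesion response and maximum tumor burden decrease suggest so. But the DOR sentence is limited to responses that have not ended, and a programmer following it would not censor a subject who died.

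Three stronger readings are tempting and are not supported:
- **That every switched responder who dies becomes durable.** The timing conditions rule this out; the subject who dies on day 230 above is not durable.
- **That DRR is overstated by some general percentage.** The documents give neither the share of responders who switch before 6 months nor their survival afterwards, and the effect grows with follow-up. Any figure computed among responders would also have to be multiplied by the response rate, because DRR is a percent of subjects.
- **That PFS has the same fault.** "PFS is defined as the interval from first dose date to the earlier event of confirmed PD or death from any cause", and its censoring rule has no new-therapy cut-off for anyone, so the split between dead and living written into DOR is not written there. Counting all deaths in PFS is a defensible choice, and censoring them at a switch could be informative.

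**Conclusion.** The gap is real on the text as written, and I found nothing elsewhere in either document that closes it. Under the three conditions above, a switched responder is durable if dead and not durable if alive. The effect is 4.8 points of DRR per subject at n=21 and 10 points at n=10. The total cannot be derived and depends on the data cutoff.

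Only the secondary, descriptive endpoints DRR and DOR are affected. The primary ORR test and the Stage 1 futility rule are not, and no decision rule uses DRR or DOR. This should be fixed, but it does not threaten the trial's main conclusion.

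**What to change.** In SAP section 5, under Duration of Response, count a death as the end of response only if it occurs before the first subsequent anticancer therapy. Otherwise censor DOR at the last evaluable assessment before that therapy, for dead and living subjects alike. Derive DRR from that DOR. Leave PFS as it is.

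The cost is a sentence or two and one derivation, with no new data. It brings DOR into line with the cut-off the SAP already uses for ORR and lesion response. The downside is that DRR and DOR may come out slightly less favourable.
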